2.3.1.10 Endurance Shuttle Box and Block Test (ESBBT)

ESBBT is an endurance test for moderately affected patients with SMA. Patients are instructed to repeatedly perform the original Box and Block Test at 75% of their individual maximum speed. The shuttles refer to the set speed marked by auditory cues, with the test ending when the patient missed 2 consecutive beeps. The primary outcome parameter is ‘time to limitation (Tlim)’ being the time a task can be maintained at the pre-set intensity. Maximal test duration is 20 minutes (Stam 2018). Non-ambulant patients who score >3 on Item A of the RULM at Screening will perform the ESBBT at Screening and all subsequent assessments. If a patient maxes out of an endurance test, the PT Advisory Board will be consulted to potentially change assessment designation. The ESBBT will be completed by patients who are or will turn 8 years of age or older during the study. Patients who turn 8 years of age in Extension Periods A or B who score >3 on Item A of the RULM at Screening should perform the ESBBT as early as possible (preferred to begin at E1) and all subsequent visits until the end of the study.

2.3.1.11 Pediatric Evaluation of Disability Inventory Computer Adaptive Test (PEDI-CAT)

A caregiver (who may or may not be a parent and/or legal guardian) must complete the PEDI-CAT Assessment. The PEDI-CAT Assessment should not be administered if a caregiver is not present. The PEDI-CAT Assessment should not be administered to the patient. The PEDI-CAT is a questionnaire completed by the caregiver that assesses the patient’s ability to perform daily functions (Haley 2005). The PEDI-CAT is filled out by the caregiver in a location where they are not watching the patient perform any functional assessment tests. The same

caregiver must fill out the assessment throughout the study duration. The answers are scored on a 4-point scale (unable to easy). The test is suitable to assess function in newborns to 21-year-olds; this questionnaire should be completed throughout the duration of the study (regardless of age). Properties of the PEDI-CAT have been studied in the SMA population. A Rasch analysis with results published in 2016 revealed that the distribution of abilities for the Mobility and Daily Activities domains of the PEDI-CAT are best represented in the Type 2 and Type 3 populations (Pasternak 2016). As the PEDI-CAT is an age-dependent questionnaire, a patient's full date of birth is required for accurate assessment.

2.3.1.12 Patient-reported Outcomes Measurement Information System (PROMIS)

The PROMIS is a person-centered measure intended to be completed by the patient or parent proxy without help from anyone (Ader 2007). The PROMIS includes 8 items and achievable range is [8, 40]. The fatigue profile domain measures a range of symptoms, from mild subjective feelings of tiredness to an overwhelming, debilitating, and sustained sense of exhaustion. The self-report measures are suitable for children 8-17 years old and the parent proxy report measures are suited for children 5-17 years old. If a caregiver completes this form, the same caregiver must complete the form throughout the study duration. Patients age 18 through 21 will complete an adult form of PROMIS. The PROMIS will be completed by patients who are or will turn 5 years of age or older at the time of the baseline assessment; the same questionnaire used at Screening should be used throughout the duration of the study (regardless of age).

The PROMIS assessments will be analyzed separately for each type of assessment identified as follows: adult form assessments, pediatric form assessments, and parent proxy assessments.

2.3.2 Safety Endpoints

In this study, safety will be evaluated based on occurrence of:

- Treatment-emergent adverse events (TEAEs) and serious adverse events (SAEs); and
- Concomitant medications.

or changes from baseline in the following parameters:

- Vital signs, including blood pressure, heart rate, body temperature, and respiratory rate;
- Height and weight;
- Physical examinations;
- Laboratory assessments (hematology and coagulation, serum chemistry, urinalysis);
- 12-lead electrocardiogram (ECG); and
- Concomitant medications.

2.3.2.1 Adverse Events

An AE is any untoward medical occurrence in a patient or clinical trial patient administered a pharmaceutical product that does not necessarily have to have a causal relationship with the treatment administered. An AE can therefore be any unfavorable or unintended sign (including an abnormal laboratory finding), symptom, or disease temporally associated with the use of a medicinal product, whether or not it is related to the medicinal product.

- AEs may be new events or may be pre-existing conditions that have become aggravated or have worsened in severity, seriousness or frequency from Baseline at any time during the study.
- AEs may be clinically significant changes from Baseline in physical examination, laboratory tests, or other diagnostic investigation (e.g., laboratory results, x-ray findings).

Adverse events will be coded using the Medical Dictionary for Regulatory Activities (MedDRA) Version 23.0 or later.

The severity of AEs will be graded using the National Cancer Institute (NCI) Common Terminology Criteria for Adverse Events (CTCAE), Version 5.0. The causal relationship between the study drug and the AE will be assessed using one of the following categories:

- Not Related: Factors consistent with an assessment of Not Related include:
 - Temporal relationship is lacking (e.g., the event did not occur within a reasonable time frame following administration of the study drug); or
 - Other causative factors more likely explain the event (e.g., a pre-existing condition, other concomitant medications).
- Related: Factors consistent with an assessment of Related include:
 - There is a positive temporal relationship (e.g., the event occurred within a reasonable time frame following administration of study drug); or
 - The AE is more likely explained by the investigational product than by another cause (e.g., the AE shows a pattern consistent with previous knowledge of the investigational product or the class of the investigational product).

2.3.2.2 Treatment-Emergent Adverse Events

Treatment-emergent adverse events (TEAEs) are defined as those AEs satisfying one of the following:

- Occur after the first administration of study drug; or
- Occur prior to the administration of study drug and worsen in severity/grade or relationship to investigational medication after the administration of study drug.

2.3.2.3 Serious Adverse Events

An SAE is any adverse event occurring at any dose that results in any of the following outcomes:

- Death
- Life-threatening experience; Note: “Life-threatening” refers to a situation in which the patient was at risk of death at the time of the event; it does not refer to an event that might have caused death if it were more severe.
- Inpatient hospitalization or prolongation of existing hospitalization. The following are excluded as per this criterion:
 - Emergency room visits/hospital admissions for AEs less than 24 hours in duration do not meet SAE criterion unless they meet any of the other SAE criteria in this list.
 - A scheduled or elective hospitalization for medical/surgical procedure planned prior to informed consent for a pre-existing condition that has not worsened from Baseline during participation in the study. However unexpected complications

and/or prolongation of hospitalization that occur during elective surgery should be recorded as AEs and assessed for seriousness. Admission to the hospital for social or situational reasons (i.e., no place to stay, too far away to come for hospital visits, respite care) will not be considered inpatient hospitalizations.

- Persistent or significant disability or incapacity or substantial disruption of the ability to conduct normal life functions
- Congenital anomaly or birth defect
- Is considered to be an important medical event: Important medical events are those that may not be immediately life-threatening or result in death or hospitalization but may jeopardize the patient or may require intervention to prevent one of the outcomes listed in the definition above. Examples of such medical events include allergic bronchospasm requiring intensive treatment in an emergency room or at home, blood dyscrasias or convulsions that do not result in inpatient hospitalizations, or the development of drug dependency.

2.3.2.4 Vital Signs

Vital signs include blood pressure, heart rate, body temperature, and respiratory rate. Vital signs will be collected according to the schedule of assessments provided in Table 3, Table 4, and Table 5.

2.3.2.5 Height, Weight and Body Mass Index (BMI)

Weight will be collected within 48 hours of each dose in order to calculate weight-based dosing, and height will be collected at visits where the motor function outcome measures are conducted.

Standing height will be collected for all individuals who are able to independently stand.

Surrogate height may be estimated using ulna length if the patient is nonambulatory or needs standing support.

The Gauld's equation (Gauld 2004) that is used for calculated height (in cm) using ulna length, for males:

$$\text{Estimated height} = (4.605 * \text{ulna length}) + (1.308 \times \text{age}^*) + 28.003$$

and for females:

$$\text{Estimated height} = (4.459 * \text{ulna length}) + (1.315 \times \text{age}^*) + 31.485$$

Where age^* is the patient's age if under 18, and 18 if patient is 18 or older.

The BMI will be derived as,

$$BMI = \frac{\text{Weight in kg}}{(\text{Height in cm} / 100)^2}$$

2.3.2.6 Physical Examination

A complete physical examination will be performed by the Investigator or a qualified designee according to the schedule of assessments provided in Table 3, Table 4, and Table 5. The findings of each examination will be recorded on the source documents and eCRF. The physical examination will include an assessment of the following: general appearance, skin, lymph nodes,

head-eyes-ears-nose-throat, neck, abdomen, extremities, and the respiratory, cardiovascular, musculoskeletal, and neurologic body systems.

2.3.2.7 *Electrocardiogram*

A 12-lead ECG will be collected at the times indicated in Table 3, Table 4, and Table 5. ECGs are to be performed with the patient having rested for at least 5 minutes before each reading. ECGs are to be performed in triplicate, each approximately 1 to 2 minutes apart. On infusion days, ECG will be collected within 2 hours prior to the start of the infusion. ECGs will be sent to a central reading vendor for assessment.

2.3.2.8 *Laboratory Testing*

Laboratory testing (eligibility screening, serum chemistry, hematology, urinalysis, and coagulation, PK and PD sample draw, and ADA testing) will be performed using established methods at the times indicated in Table 3, Table 4, and Table 5. All safety laboratory analyses will be performed at a central laboratory.

The following hematology and coagulation parameters will be assessed:

- Hemoglobin
- Red blood cell count
- Hematocrit
- White blood cell count with differential
- Absolute platelet count
- Mean corpuscular hemoglobin
- Mean corpuscular hemoglobin concentration
- Mean corpuscular volume
- Activated partial thromboplastin time (APTT)
- Prothrombin Time/International Normalized Ratio (PT/INR)

The following serum chemistry parameters will be assessed:

- | | |
|--------------------------------|----------------------------|
| • Albumin | • Pregnancy (females only) |
| • Alanine aminotransferase | • Lactate dehydrogenase |
| • Alkaline phosphatase | • Magnesium |
| • Aspartate aminotransferase | • Phosphate |
| • Bilirubin (total and direct) | • Potassium |
| • Blood urea nitrogen | • Sodium |
| • Calcium | • Total cholesterol |
| • Carbon dioxide | • Total protein |
| • Chloride | • Triglycerides |
| • Creatinine | • Uric acid |
| • Creatine phosphokinase | |
| • Gamma-glutamyl transferase | |
| • Glucose | |

The following urinalysis parameters will be assessed:

- Bilirubin
- Blood microscopy (if urinalysis is abnormal)
- Glucose
- Ketones
- Nitrite
- pH
- Protein
- Specific gravity

2.3.3 Pharmacokinetics (PK), Pharmacodynamics (PD), and Immunogenicity Endpoints

2.3.3.1 Pharmacokinetics Blood Sample Collection

Blood samples for the measurement of SRK-015 concentrations will be obtained prior to study drug infusion as indicated in the schedule of assessments in Table 3, Table 4, and Table 5. In the Treatment Period, the 2-hour (\pm 1 hour) postdose (from the stop of the infusion) sample collection on Day 0, Day 140, and Day 336 must be collected via peripheral venipuncture. In Extension Periods A and B, the 1-hour (+30-minute window) postdose (from the stop of the infusion) sample collection on Day 700 and Day 1008 must be collected via peripheral venipuncture.

Each collected sample will be split into approximately equal volume sample sets to allow for retesting, if required. Aliquots from the PK blood samples may be used for additional immunogenicity or PD testing as appropriate, and Baseline and postdose samples may be used to support PK, PD and/or ADA assay validation.

2.3.3.2 Pharmacodynamics Blood Sample Collection

Blood samples will be collected for the measurement of latent myostatin levels. These blood samples will be obtained prior to infusion as indicated in the schedule of assessments in Table 3, Table 4, and Table 5. The 2-hour (+30-minute window) postdose (from stop of infusion) sample collection on Day 0 must be collected via peripheral venipuncture.

Each collected sample will be split into approximately equal volume sample sets to allow for retesting, if required. Aliquots from the PD blood samples may be used for additional PK or immunogenicity testing as appropriate, and Baseline and postdose samples may be used to support PK, PD, and/or ADA assay validation.

2.3.3.3 Immunogenicity Blood Sample Collection

Blood samples for the measurement of anti-SRK-015 antibodies will be obtained prior to infusion as indicated in the schedule of assessments in Table 3, Table 4, and Table 5.

Each collected sample will be split into approximately equal volume sample sets to allow for retesting, if required. Aliquots from the immunogenicity samples may be used for additional PK or PD testing as appropriate, and Baseline and postdose samples may be used to support PK, PD, and/or ADA assay validation.

3 STATISTICAL METHODOLOGY

3.1 General Considerations

The primary analysis will focus on safety and efficacy data up to V15 (Day 364), which will be referred as the 12-month analysis. The interim analysis will focus on safety and efficacy data up to V8 (Day 168). Extension Period analyses where the focus will be safety and efficacy data in

the Extension Period will be carried out separately. The method used in the 12-month analysis will be applied for the Extension Periods and the analyses of the Extension periods will be considered exploratory.

3.1.1 Analysis Day

Analysis day will be calculated using the first dose date of study drug as the reference. Analysis day = date - date of first dose +1 according to Clinical Data Interchange Standards Consortium (CDISC) standards. The day the patient takes the first dose is Analysis Day 1. The day before Analysis Day 1 is Analysis Day -1.

3.1.2 Analysis Visits

Scheduled post-baseline assessments will be assigned to an analysis visit based on the visit captured in EDC. Unscheduled post-baseline and early termination assessments for motor function outcome measures will be assigned to an analysis visit based on the calculated Analysis Day and windows defined in the following table:

Visit	Analysis Visit	Analysis Day Target	Analysis Day Window
Visit 4/Day 56	Visit 4/Week 8	57	44 - 99
Visit 6/Day 112	Visit 6/Week 16	113	100 – 155
Visit 8/Day 168	Visit 8/Week 24	169	156 - 211
Visit 10/Day 224	Visit 10/Week 32	225	212 - 267
Visit 12/Day 280	Visit 12/Week 40	281	268 – 351
Visit 15/Day 364	Visit 15/Week 52	365	352 - 379
Visit 16/Day 392	Visit 16/Week 56	393	380 - 421
Visit 17/Day 448	Visit 17/Week 64	449	>421
Visit E1/Day 364	Visit E1/Week 52	365	352-379
...		...	(target date-13 days to the next target date - 14 days)

For each analysis visit, if a scheduled visit is captured in EDC, then the measurement from this scheduled visit will be used as the measurement for the analysis visit. If no scheduled visit is captured in EDC, the unscheduled measurement within the window closest to the target date will be used. Visits that occurred outside a +/- 28-day window of the target date used as analysis visits will be listed. For safety measurements, unscheduled and ET visits will not be re-assigned and will be listed, and the ET visit will be summarized separately.

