2.2.4 Visits and Assessments

Assessments and visit windows at each scheduled visit are specified in the Study Schedule of Assessments (Tables 3-5). For patients who prematurely discontinue from the study during the Treatment Period, all assessments scheduled for V17 (Day 448) will be completed at the Early Termination (ET) visit, if possible; for patients who discontinue from the study during Extension Period A, all assessments scheduled for E15 (Day 784) would be completed at the ET visit for Extension Period A; for patients who discontinue from the study during Extension Period B, all assessments scheduled for EB15 (Day 1176) would be completed at the ET visit for Extension Period B.

Due to the pandemic of Coronavirus disease 2019 (COVID-19), study visits for some patients were delayed or cancelled. The sites were given the following instructions:

- If a visit window exceeds 56 days from the latest patient visit, that visit should be skipped.
- If a visit window exceeds 84 days from the latest patient visit, two consecutive visits should be skipped.

These guidelines hold true except if the patient is at Visit 15 (Day 364); regardless of the duration from the latest patient visit, Visit 15 (Day 364) should not be skipped.

If the skipped visit is one where motor function outcome measures should be conducted (i.e., Visit 4 [Day 56], Visit 6 [Day 112], Visit 8 [Day 168], etc.), motor function outcome measures are to be conducted at the next scheduled visit either as part of the visit or as unscheduled assessments.

If it is believed that a patient may miss 3 consecutive visits, the Medical Monitor should be contacted to provide guidance on a case-by-case basis.

Examples:

If a patient is seen on 01Apr2020 for Visit 7 (Day 140) but cannot return to the site until 28May2020 (57 days from latest visit), then Visit 8 (Day 168) will be considered as skipped. When the patient is seen on 28May2020, Visit 9 (Day 196) will be conducted and the PT assessments will be performed as unscheduled assessments.

If a patient is seen on 01Apr2020 for Visit 7 (Day 140) but cannot return to the site until 25Jun2020 (85 days from the latest visit), then Visit 8 (Day 168) and Visit 9 (Day 196) will be considered as skipped. When the patient is seen on 25Jun2020, Visit 10 (Day 224) will be conducted and motor function outcome measures will be performed per protocol.

Table 3: Study Schedule of Assessments: Treatment Period

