5.1.2 Safety and Efficacy Interim Analysis

Prespecified interim analyses to evaluate the initial safety and efficacy of SRK-015 in SMA patients was planned in the protocol when all enrolled patients complete V8 (Day 168) or are terminated from the study. Interim analyses were to be performed on the selected efficacy endpoints up to V8 (Day 168), in addition to available selected safety outcomes and PK and PD results (see 5.1.1). Due to COVID-19, some patients delayed or skipped V8 (Day 168). The study sites were given instructions that if the actual visit date is > 56 days but ≤ 84 days from the previous visit then one visit is considered skipped; if >84 days but ≤ 112 days, two visits are considered to be skipped. In addition, some sites kept patient dosing on schedule (no skipping) but did not perform outcome assessment due to PT department closure. If the outcome assessment is skipped regardless of dosing, the site was instructed to perform an outcome assessment at the next visit, which may be unscheduled. Considering these impacts, the safety and efficacy interim analyses will target all patients who have either a V8 (Day 168) measurement or a post V8 (Day 168) visit if V8 (Day 168) is skipped, but will exclude patients with numerous skipped visits.

The following strategies will be adopted to analyze the primary endpoints and to address the COVID-19 impact, where applicable. Because some cohorts may be affected more than others, the strategies may not apply to all cohorts:

- 1) Use the earliest of V8 (Day 168), V9 (Day 196), and V10 (Day 224) data, where available, and for those not having V8-V10 not due to COVID-19, LOCF will be applied.
- 2) For sites closed or patients experiencing travel restrictions/difficulties due to COVID-19 and patients not having V8 (Day 168), V9 (Day 196) and V10 (Day 224) data, those visits will be excluded from the analysis.
- 3) Descriptive analysis will include the earliest of V8/V9/V10.

Descriptive statistics will be used for Efficacy and Safety endpoints at this interim analysis. For continuous efficacy endpoints, the 95% CI of change from Baseline will also be reported.

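### SAP 3.1.2 lets an unscheduled motor test count only when the scheduled visit is absent from EDC, so make-up tests after dosed-but-untested visits can go unused, mainly at secondary time points

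*Combined protocol and SAP*

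**What the plan says.** SAP 3.1.2 works in two steps. The first is assignment: "Unscheduled post-baseline and early termination assessments for motor function outcome measures will be assigned to an analysis visit", using the Analysis Day and a table of windows. The second chooses one value to analyse: "if a scheduled visit is captured in EDC, then the measurement from this scheduled visit will be used as the measurement for the analysis visit". The alternative is: "If no scheduled visit is captured in EDC, the unscheduled measurement within the window closest to the target date will be used". No sentence covers a visit that is in EDC but has no motor score.

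SAP 5.1.2 describes that case as a consequence of COVID-19: "some sites kept patient dosing on schedule (no skipping) but did not perform outcome assessment due to PT department closure". Where a test was missed, whether or not the patient was dosed, "the site was instructed to perform an outcome assessment at the next visit, which may be unscheduled". SAP 2.2.4 gives a parallel instruction for skipped visits: "motor function outcome measures are to be conducted at the next scheduled visit either as part of the visit or as unscheduled assessments".

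For the interim analysis SAP 5.1.2 has a separate rule for V8: "Use the earliest of V8 (Day 168), V9 (Day 196), and V10 (Day 224) data, where available". SAP 3.1.7.2 repeats it, again for the interim only. For the 12-month analysis, SAP 3.1.7.2 says that LOCF applies in the descriptive analyses, but its general LOCF sentence is limited to patients lost to follow-up.

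**The concern.** The fallback depends on the wrong condition. A patient who came in, was dosed and was not tested has a scheduled visit in EDC, so the first branch applies and finds no measurement. The second branch, which would admit the make-up test, needs the visit to be absent. The sites collected that test on instruction, while the patient was on drug, and it sits in the right window, yet the rule as written does not select it.

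At stake are the by-visit changes and responder proportions in groups of 10 to 20 patients. The score for that visit is then either missing or an older value carried forward. The SAP does not settle which, because a dosed patient is not lost to follow-up.

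**Working it through.** **Inputs.** Targets and windows come from the table in SAP 3.1.2. Analysis Day (AD) is study day + 1 (SAP 3.1.1). The visit window is ±7 days (SAP Table 3, note a). The SD of 2.5 for HFMSE change is from SAP 2.2.3.

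**Step 1: reproduce the plan's windows.** The formula printed for later rows is "target date-13 days to the next target date - 14 days". Applied to V4 through V15 it gives:
- V4: 57 − 13 = 44 to 113 − 14 = 99
- V6: 113 − 13 = 100 to 169 − 14 = 155
- V8: 169 − 13 = 156 to 225 − 14 = 211
- V10: 225 − 13 = 212 to 281 − 14 = 267
- V12: 281 − 13 = 268 to 365 − 14 = 351
- V15: 365 − 13 = 352 to 393 − 14 = 379

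All six match the table.

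**Step 2: locate a make-up test done at the next visit** (AD = study day + 1, ±7).

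| Untested visit | Window (AD) | Next visit | Make-up AD | Inside? |
|---|---|---|---|---|
| V4 | 44–99 | V5, Day 84 | 78–92 | yes |
| V6 | 100–155 | V7, Day 140 | 134–148 | yes |
| V8 | 156–211 | V9, Day 196 | 190–204 | yes |
| V10 | 212–267 | V11, Day 252 | 246–260 | yes |
| V12 | 268–351 | V13, Day 308 | 302–316 | yes |
| V15 | 352–379 | V16 or E2, Day 392 | 386–400 | no |

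**Step 3: apply the selection rule literally.**
- *Dosed, not tested.* V6 is dosed on Day 112 and the unscheduled make-up is done on Day 140, so AD 141, inside 100–155. V6 is in EDC, so the fallback condition is false and the test is not selected.
- *Visit skipped.* In the 57-day example in SAP 2.2.4, with V7 at its nominal AD 141, the return visit is at 141 + 57 = AD 198, inside 156–211. V8 is not in EDC, so the test is selected.

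The two patients differ only in whether a dosing visit was recorded.

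**Step 4: how Day 364 could be reached.**
- *Extra test.* An unscheduled test on AD 352–379 is passed over if V15 is in EDC without a score. If LOCF then supplies the V12 score (target AD 281), that score is 352 − 281 = 71 to 379 − 281 = 98 days older than the test passed over.
- *LOCF through V12.* V12 is dosed but untested, the make-up at V13 (AD 309) is not selected, and there is no Day 364 score. If LOCF draws on analysis-visit scores, it carries V10 (target AD 225), which is 309 − 225 = 84 days older than the make-up.

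**Step 5: illustrative loss of precision.** No count of affected patients is given. Assume 1 or 2 scores lost at a time point, no imputation, and SD 2.5. The 95% CI half-width is 2.5 × t(0.975, n − 1)/√n.
- From n = 10: 1.79, then 1.92 (n = 9) and 2.09 (n = 8); +7% and +17%
- From n = 15: 1.38, then 1.44 and 1.51; +4% and +9%
- From n = 20: 1.17, then 1.20 and 1.24; +3% and +6%

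If LOCF fills the gap, n does not fall and these figures do not apply. The SD is given for HFMSE only, so they say nothing about RHS in Cohort 1.

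**The case against.** The best defence is that nothing in SAP 3.1.2 tells anyone to discard a make-up test. Assignment to windows is unconditional, and the selection sentence presupposes that the scheduled visit produced a measurement. Where it did not, the unscheduled value is the only candidate, and a sensible programmer would take it. This stands in part: the defect is a gap in wording, not an instruction to drop data. But the SAP separates visits from assessments elsewhere. The skipped-visit example in 2.2.4 conducts V9 while recording the motor tests as unscheduled, and 5.1.2 speaks of assessments missed regardless of dosing. Programming specifications are in stand-alone documents (SAP 7), so two programmers could produce different datasets from this text.

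Two further objections stand. V4 to V12 are secondary, descriptive time points with no formal testing (SAP 3.1.5). And the report of dosing without testing comes in the interim section, around V8, and does not name the other visits affected.

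A reader might infer that the rule removes instructed make-up tests from the primary Day 364 analysis. The documents do not support that. The next visit after V15 is Day 392, at AD 386–400, which is outside 352–379 whichever way the rule is worded. SAP 5.2 says only that V15 was delayed or skipped, and if it was skipped the existing fallback works. A test done within a week of Day 364 could also be entered under V15 itself, since assessments may be spread over days within the visit window, subject to their own timing rules.

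**Conclusion.** The point holds as a correctable gap in the analysis-visit rule. Read as written, in-window make-up tests after dosed-but-untested visits are not selected at V4, V6, V10 and V12, nor at V8 in the 12-month by-visit summaries. The interim V8 analysis is protected by its own rule.

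The consequence falls mainly on secondary time points. For Day 364 it is confined to the two routes in step 4, neither of which the documents show to have occurred.

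The size cannot be fixed from the documents. On an assumed one or two lost scores, intervals widen by 3% to 17% depending on group size, and only if the score is left missing. The conclusion rests on the literal reading of the selection sentence. On the looser reading the data are used, but the text still needs to say so.

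**What to change.** Replace the selection sentences in SAP 3.1.2 with:

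> For each motor function measure and analysis visit, use the non-missing result from the scheduled visit. If there is none, whether or not the visit is captured in EDC, use the non-missing result within the window closest to the target day, whether recorded as unscheduled, as ET, or at a visit where motor testing was not scheduled (e.g., V7, V9, V13).

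The last clause is needed because SAP 2.2.4 lets a make-up be recorded as part of the next visit, and those intermediate visits have no row in the window table. A rule limited to unscheduled and ET results would still miss them. The SAP should also say how a Day 364 make-up obtained at Day 392 is treated, since the rewording does not bring it into the window.

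The cost is a short rewording and one programming condition, with no new data. Protocol 6.2 gives a 12-month database lock of 19 January 2021. For those results the practical step is to confirm how the program applied the rule, list any make-up tests passed over, and report this in the CSR, where SAP 1 places post-lock deviations. The rewording also matters going forward, because SAP 3.1 applies the 12-month method to the Extension Periods.
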